#### **4.7 Screen failure procedures**

Study participants will be checked to determine if they meet the inclusion and exclusion criteria. Those that are not eligible will be excluded from the study. If the study coordinators are not able to contact study subjects in the follow-up phone calls they will be considered as “loss to follow-up” and no longer enrolled in the study.

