Baseline measurements will be taken prior to intervention so that each subject may serve as his/her own control. 12-hour fasting blood and serum will be drawn pre- and post-intervention for each subject by a licensed phlebotomist at the UNC Family Medicine Lab and under the direction of [name], the co-I. Each blood sample will be the size of 10 10mL plasma and serum tubes (9 plasma tubes + 1 serum tube) to ensure that enough B cells are collected from PBMCs for activations (see section 4.1 below). Therefore, a total of 10 tubes or ~100 ml of blood will be drawn twice during the study, 4 weeks apart. Finally, each subject will have his/her height (ft), body weight (lbs), blood pressure (mmHg), and pulse (bpm) taken at baseline and 4 weeks of intervention.

Follow up: Subjects will have two face-to-face visits and two phone contacts during the study. The first visit will be at baseline (pre-intervention) and the second visit will conclude the study (post-intervention). We will continuously monitor subject health status throughout the study via phone contact at the end of week 1 and week 3 following the start of supplementation. At the end of the study, all patients will follow up in a routine manner as designated by their physician at UNC Family Medicine.

Unscheduled Visits: If the study coordinator relays health concerns to [name] that will necessitate in-person visit.

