#### **4.6 Subject Completion/ Withdrawal procedures**

Subjects will be compensated \$250 cash for their participation and completion of the study (\$100 at baseline visit + \$150 at week 4 visit upon completion). No prorated compensation will be applied for this pilot study. This amount of compensation is not deemed coercive; the incentive is meant to compensate subjects for their time in the study which include two study visits, two phone visits, and two blood draws.

This is a voluntary research study. Refusal to participate or withdrawal of participation and/or consent can occur at any time, for any reason. Subjects may be withdrawn if: (1) they experience intolerable adverse reactions or allergic reaction to study supplement or (2) are not at least 90% compliant with taking study supplement during the 4 weeks active phase. In the event of withdrawal, all personal health information (PHI), electronic or hard copy, will be immediately purged and permanently destroyed. Withdrawal or

refusal will not influence ability, timing, or quality of clinical care, type of clinical care administered, standing with UNCHC system, or ability to participate in future research studies. The investigators also have the right to stop participation at any time. This could be because participants have chosen to stop supplementation, or have failed to follow instructions or because the entire study has been stopped.

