## **7 STUDY INTERVENTION**

The “SPM Active” supplement will be shipped all at once from Metagenics at room temperature to the UNC Family Medicine clinic with expiration that covers the full duration of the intervention. Study participants will be instructed to keep the supplement at room temperature. Subjects who have consented to the study will receive the exact number of tables required for the study. They will be instructed to consume 4 capsules per day (2 capsules with breakfast and 2 with dinner) of “SPM Active” for 4 weeks. Each capsule contains 145 mg of SPMs for a total daily dose of 580 mg. There are 3 metabolites of the SPM family in the capsule, which are 17-HDHA (40mg) + 14-HDHA (80mg) + 18-HEPE (25mg). All three metabolites feed into pathways shown to improve insulin resistance and all three metabolites are decreased in obese subjects. The rationale for the dosing and time of intervention is based on the recommendations by the manufacturer. Appropriate dosing will be monitored with the follow-up phone calls at weeks 2 and 3. Participants who have chosen to stop supplementation, or have failed to follow supplement instructions will be withdrawn from the trial.

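### Subjects who miss calls or stop the supplement can leave before the only post-treatment draw, and the PHI purge on withdrawal conflicts with adverse-event follow-up

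*Combined protocol and SAP*

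**What the plan says.** **Leaving the study.** Three sections deal with it.

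- Section 4.7: "If the study coordinators are not able to contact study subjects in the follow-up phone calls they will be considered as" lost to follow-up, and their enrolment ends. It does not say whether one missed call is enough or both must be missed.
- Section 7: "Participants who have chosen to stop supplementation, or have failed to follow supplement instructions will be withdrawn from the trial".
- Section 4.6 treats stopping and failing instructions as grounds on which the investigators have a right to end participation: "This could be because participants have chosen to stop supplementation, or have failed to follow instructions or because the entire study has been stopped". Withdrawal is also only a possibility for subjects who "are not at least 90% compliant with taking study supplement during the 4 weeks active phase".

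**Contacts and samples.** Section 3.1 (Overview of Study Phases) says: "Subjects will have two face-to-face visits and two phone contacts during the study". The second visit closes the study and supplies the only post-treatment blood sample. The calls fall at weeks 1 and 3 in the Synopsis and Sections 3.1, 4.5 and 9, but at weeks 2 and 3 in Sections 2.2 and 7.

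**Analysis.** Section 6 plans paired pre/post tests. It names no analysis set and gives no rule for missing samples.

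**Records.** Section 4.6 says: "Subjects may be withdrawn if: (1) they experience intolerable adverse reactions or allergic reaction to study supplement", and then: "In the event of withdrawal, all personal health information (PHI), electronic or hard copy, will be immediately purged and permanently destroyed". Section 9 requires a log of adverse events kept by patient throughout the study, and follow-up of clinically significant events until they resolve. Section 10 keeps the samples and data of subjects lost to follow-up. It does not mention withdrawn subjects.

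**The concern.** In a paired design, a subject without the closing draw contributes nothing to the primary comparison, even if willing to attend. Followed as written, Sections 4.7 and 7 can remove such subjects for an administrative reason (a missed call) or for poor adherence. With no control arm, the pre/post change would then describe mainly subjects who could be reached and who took the supplement. That may be a reasonable target, but the plan does not say it is the target. The same subjects would also miss the adverse-event screen that Section 9 places at the week-4 visit.

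The purge is a separate matter. An intolerable or allergic reaction is the first listed reason for withdrawal, and withdrawal triggers immediate destruction of PHI. The subjects whose events most need following are therefore those whose study identifiers would be destroyed.

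**Working it through.** **1. The plan's own figures.** Section 6.4 raises 18 to 24 for loss to follow-up. No rate is stated; the implied one is (24 − 18)/24 = 25%, and 18/(1 − 0.25) = 24, so the arithmetic is consistent. The claim of more than 80% power at n=9 cannot be reproduced, because the standard deviation of the within-subject differences is not given. It can only be used as an anchor.

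**2. Power when pairs are lost.** Inputs: paired t-test; family-wise error of 5% over three metabolites (Section 6.4), taken here as α = 0.05/3 = 0.0167 each; two-sided (Section 6.1, Aim 1a). The equal split, and two-sidedness in the power calculation, are assumptions. With standardized effect d (mean change divided by SD of differences),

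power(n) = P(|T| > t for 1 − α/2 on n − 1 df), where T is noncentral t with n − 1 df and noncentrality d√n.

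Solving for d at n=9 gives d = 1.323 for exactly 80% and d = 1.509 for exactly 90%. Holding d fixed:

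| Completers | Anchor 80% at n=9 | Anchor 90% at n=9 |
|---|---|---|
| 7 (one sex) | 60.6% | 73.4% |
| 8 (one sex) | 71.5% | 83.3% |
| 9 (one sex) | 80% | 90% |
| 14 (pooled) | 97.6% | 99.5% |
| 18 (pooled) | 99.7% | 99.97% |

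The n=8 figure under the 80% anchor is 0.7147, that is 71% in whole numbers.

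**3. How much the undefined call trigger matters.** The documents give no missed-call rate, so the rates here are assumptions: miss chance p per call of 5%, 10% or 20%, with correlation r between the two calls of 0 or 0.5.

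P(both missed) = p² + r·p(1 − p); P(at least one missed) = 2p − P(both missed). Multiplying by 24:

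| p | One missed call ends enrolment (r = 0.5 to 0) | Both must be missed (r = 0 to 0.5) |
|---|---|---|
| 5% | 1.8 to 2.3 of 24 | 0.1 to 0.6 of 24 |
| 10% | 3.5 to 4.6 | 0.2 to 1.3 |
| 20% | 6.7 to 8.6 | 1.0 to 2.9 |

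Under the one-call reading with independent calls, all six allowed losses are used when 1 − (1 − p)² = 0.25, so p = 13.4%.

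**4. The purge against adverse-event follow-up.** No arithmetic applies.

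- Section 4.6: on withdrawal, destruction covers all PHI, in every medium, at once. An intolerable or allergic reaction is a listed ground for withdrawal. No exception is written.
- Section 9: the log is assigned to each patient, and significant events are followed to resolution. No exception is written for withdrawn subjects.

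Both cannot be carried out for a subject withdrawn because of an unresolved reaction, since following that person requires identifiers that Section 4.6 has destroyed.

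**The case against.** The case on the other side is substantial. This is a pilot, and Section 2 calls it a bioavailability study; measuring uptake in people who took the capsules is a natural target, and the 90% rule comes close to stating it. The plan already allows for six losses. Section 4.7 refers to the calls in the plural, which reads at least as naturally as failure across both; under that reading the highest loss shown is 2.9 of 24. A subject who cannot be reached may not attend a draw either. All of this stands, and it is why the first part is an improvement and not an error.

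Four stronger readings are tempting, and the documents do not support them.

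- *The primary analysis is underpowered or shown to be biased.* The pooled test is barely affected, and neither the direction nor the size of any bias can be derived.
- *Every such subject is removed before the draw.* Section 4.6 is discretionary, and adherence in the last week may be known only at the closing visit.
- *Data of subjects lost to follow-up are destroyed.* Section 10 keeps them; the purge concerns withdrawn subjects.
- *All trial data of withdrawn subjects are destroyed.* Section 4.6 names PHI. Tubes carry a research code (Section 5) and de-identified data sit in REDCap (Section 10), so coded adverse-event entries may survive.

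On the purge, routine care at the clinic offers some protection, and the consent pages and the Part C mentioned in Section 10 were not available to check. Neither removes the conflict between Sections 4.6 and 9 as they stand.

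**Conclusion.** Two conclusions, of different kinds.

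First, keeping the week-4 draw is a cheap improvement. As written, obtainable pairs can be lost for administrative or adherence reasons. The exposure is the by-sex analysis, which Section 6.4 gives as the reason for doubling the sample but which is run only if the sexes diverge: 71% power at n=8 and 61% at n=7, if power at n=9 is exactly 80% with two-sided α of 0.05/3. The plan says more than 80%, so these figures are on the cautious side. The actual loss cannot be sized from the documents, and no size is claimed for the gain.

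Second, the purge is wrong as written. It conflicts with the adverse-event log and follow-up in Section 9, and this needs no numerical assumption.

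The discretionary wording in Section 4.6 against the mandatory wording in Section 7, the differing call weeks and the undefined call trigger are real inconsistencies. They are tidying and do not carry the point.

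**What to change.** These changes concern data collection and records. They take no position on when the supplement should be stopped.

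1. In Sections 4.6, 4.7 and 7, state that a missed call, low adherence or stopping the supplement does not by itself end data collection. The scheduled week-4 draw is still offered unless consent is withdrawn or the investigator considers it unsuitable.
2. In Section 6, report the pre/post change in all dosed subjects with both samples and in the subset at least 90% compliant. The sponsor names the primary set in advance.
3. In Section 4.6, except from the purge the Section 9 adverse-event log and the identifiers needed for adverse-event follow-up, until resolution and subject to the consent terms. A general extension of Section 10 retention to all withdrawn subjects is not needed to resolve the conflict.
4. Tidying: reconcile Section 4.6 with Section 7 on whether withdrawal is discretionary or mandatory, reconcile the call weeks, and define in Section 4.7 what counts as failure to contact.

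Cost: protocol and consent wording; completion payments of up to about (24 − 18) × $150 = $900 if all six allowed losses attend, plus assays; and identifiers held somewhat longer for the excepted subjects. A draw of about 100 ml may not suit everyone, hence the investigator exception. The average rise may look smaller once less adherent subjects are included.

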### **5 STUDY EVALUATIONS AND MEASUREMENTS**

Samples taken from pre- and post-intervention visits will be immediately transferred to [name] ([name] Lab) for immediate processing. Tubes will be labelled with a de-identified research code and will not include any PHI. We will measure SPMs in 100µl of plasma and serum and  $2 \times 10^6$  PBMCs. PBMCs will be isolated with established protocols in our lab. The rationale for PBMCs vs. plasma and serum is to compare biomarkers for SPM uptake. We will also measure other lipid metabolites including thromboxanes, leukotrienes, prostaglandins, epoxy fatty acids, eoxins, mono-, di-, and tri-hydroxy fatty acids, and hepoxilins. Blinded samples will be shipped to our collaborator [name] (pay-for-service, see support letter) for two-dimensional reverse phase HPLC tandem mass spectrometry. Blood samples from baseline and post-intervention will be used to measure fasting glucose (mg/dL), fasting lipid panel (total cholesterol in mg/dL, LDL in mg/dL, HDL in mg/dL, triglyceride levels in mg/dL) and fasting insulin (ng/mL) through McClendon labs.

#### **5.1 Efficacy Evaluation**

There will be no efficacy evaluation due to the pre-/post- study design, which requires that data be obtained through the end of the clinical trial. However, the study may be stopped due to safety concerns (see safety evaluation section 5.2).

#### **5.2 Safety Evaluations**

Any health conditions that arise over the course of the study that were not present in the subjects prior to their enrollment will be monitored by [name] who will evaluate whether to withdraw the subject from the study.

### **6 STATISTICAL CONSIDERATION**

#### **6.1 Primary Endpoint**

The primary aim of the study is designed and powered to measure an increase in 18-HEPE, 17-HDHA, and 14-HDHA in Aim 1. At a family-wise error rate of 5% controlling for testing of three metabolites mentioned above,  $n=9$  will provide more than 80% power to detect a 50%-fold change increase in metabolite levels within each subject. We are assuming a similar effect size for both males and females and are doubling the sample size ( $n=18$ , 9 per sex) to allow us to subset the data in case we find divergent results between sexes. To account for possible loss-to-follow up, we increased the sample size from 18 to 24 ( $n=12$  male + 12 female). Power analysis was conducted assuming a paired t-test on pre- and post-treatment metabolite levels for three pre-specified metabolites. Expected variability of within subject differences in metabolite levels was assessed from a previous dataset and the median standard deviation was calculated across all

metabolites. Power analyses were calculated by [name] in the UNC Department of Biostatistics. Note that all analyses will be conducted in the R statistical software.

- **Aim 1a:** SPM lipidomic measurements will be analyzed pre/post supplementation. Each SPM metabolite's distribution will be assessed for normality and homogeneity of variance using the Shapiro-Wilks test and Bartlett test respectively. However, normality will also be assessed via a qqplot of the standardized residuals and we will visualize the distribution of our data with a histogram. In addition, to corroborate the Bartlett test we will check the homogeneity of variance of the residuals (homoscedasticity) using a scale-location plot where the square roots of the absolute values of the standardized residuals are plotted. If the metabolite's distribution satisfies the assumption of normality & homogeneity of variance then a paired two-tailed Student's T-test will be used to generate p-values corresponding to differences before and after supplementation. If the assumption of homoscedasticity is not met, the data will be analyzed using a paired Welch T-test. Another alternative would be to apply a log or square root transformation. However, if the data still fails the assumptions of normality and homoscedasticity it will be analyzed with a paired Wilcoxon rank sum test. All p-values will undergo a Benjamini-Hochberg adjustment (optimal for large-scale multiple hypothesis testing) at a false discovery rate of 5% to account for multiple hypothesis testing between metabolites.
- **Aim 1b:** Antibody concentrations measured via ELISA will be tested for the assumptions of normality and homogeneity of variance using the Shapiro-Wilks test and Bartlett test respectively. However, normality will also be assessed via a qqplot of the standardized residuals and we will visualize the distribution of our data with a histogram. In addition, to corroborate the Bartlett test we will check the homogeneity of variance of the residuals (homoscedasticity) using a scale-location plot where the square root of the standardized residuals is plotted. Data that passes both assumptions will be analyzed via a paired two sample Student T-test. Data that fails the assumption of homoscedasticity will be analyzed using a paired Welch T-test. Another alternative would be to apply a log or square root transformation. However, if the data still fails the assumptions of normality and homoscedasticity it will be analyzed with a paired Wilcoxon rank sum test. All p-values from these analyses will undergo a Bonferroni p-value adjustment (optimal for smaller-scale multiple hypothesis testing).

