## PROTOCOL SYNOPSIS

Study Title	Immunometabolic Response to Specialized Pro-Resolving Mediators in Obese Humans
Funder	Departmental funds
Clinical Phase	Pilot study
Study Rationale	
Obesity is associated with chronic, low-grade inflammation and impaired immunity, which contributes to the development of metabolic complications such as diabetes, cardiovascular disease, and increased susceptibility to infection due to impaired humoral immunity. The metabolism of immune cells has emerged as a major therapeutic target for improving chronic inflammation. Specialized pro-resolving mediators (SPMs) in particular are lipid-derived metabolites critical in orchestrating the resolution phase of inflammation. However, SPMs are lowered with obesity. The innovation lies in the study of SPMs as therapeutic agents for immune resolution of chronic inflammation that can lead to an improved humoral immune response in the obese. Our first objective is to establish the concentration of SPMs in plasma, serum and peripheral blood mononuclear cells (PBMCs) of obese subjects in response to dietary supplementation of SPMs (aim 1a). We will further determine the immunological fitness of the leukocyte pool, specifically examining B cell antibody production in response to ex-vivo stimulation (aim 1b). Finally, we will correlate metabolic profiles with SPM concentrations (aim 2). Overall, this will help us determine whether SPM supplementation mitigates the impaired humoral immune response of obese subjects and determine the use of SPMs as potential therapeutic agents for the obese.

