## 2.1 Primary Objective

Our primary objective is to compare immunological fitness pre- and post- oral SPM administration in the obese:

- **Aim 1a: To quantify SPM concentrations in plasma, serum and PBMCs before and after oral SPM supplementation.** We will measure SPMs in 100µl of plasma and  $2 \times 10^6$  PBMCs. PBMCs will be isolated with established protocols in our lab. The rationale for PBMCs vs. plasma is to compare whether SPM levels in PBMCs are higher than plasma or vice versa, indicating SPM uptake into the immune cells or lack thereof. We will also measure other lipid metabolites involved in the inflammatory resolution process including thromboxanes, leukotrienes, prostaglandins, epoxy fatty acids, eoxins, mono-, di-, and tri-hydroxy fatty acids, and hepoxilins. Blinded samples will be shipped to our collaborator [name] for two-dimensional reverse phase HPLC tandem mass spectrometry.
- **Aim 1b: To measure antibody responses of B cells in PBMC pool with *in vitro* stimulation and cytokine production before and after SPM supplementation.** B cells will be directly stimulated in the PBMC isolate to mimic their natural environment. Then, antibody concentrations will be measured from the supernatants of the cultured cells via ELISA for pre- and post-intervention samples.

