### **6.4 Sample Size and Power**

Experimental rigor is ensured through the analyses of blinded samples. The study is designed and powered to measure an increase in 18-HEPE, 17-HDHA, and 14-HDHA in Aim 1. Additional measures in Aim 2 are exploratory, but necessary for future grant applications to demonstrate the feasibility of the approach. At a family-wise error rate of 5% controlling for testing of three metabolites mentioned above, n=9 will provide more than 80% power to detect a 50%-fold change increase in metabolite levels within each subject. We are assuming a similar effect size for both males and females and are doubling the sample size (n=18, 9 per sex) to allow us to subset the data in case we find divergent results between sexes. To account for possible loss to follow-up, we will increase sample size from 18 to 24 (n=12 male + 12 female). Power analysis was conducted assuming a paired t-test on pre- and post-treatment metabolite levels for three pre-specified metabolites. Expected variability of within subject differences in metabolite levels was assessed from a previous dataset and the median standard deviation was calculated across all metabolites. Power analyses were calculated by [name] in the UNC Department of Biostatistics.

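### Aim 1a is sized at a 5% family-wise error rate for three metabolites but tested with Benjamini-Hochberg, and neither the primary matrix nor the extent of the adjustment family is stated

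*Combined protocol and SAP*

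**What the plan says.** **Sizing.** Section 6.4, with matching text in 6.1 and the Synopsis, states: "At a family-wise error rate of 5% controlling for testing of three metabolites mentioned above, n=9 will provide more than 80% power to detect" a 50% within-subject increase. The three metabolites are pre-specified. The 9 is doubled to 18, nine per sex, "to allow us to subset the data in case we find divergent results between sexes", and then raised to 24 for loss to follow-up.

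**Analysis.** Section 6.1, Aim 1a, states: "All p-values will undergo a Benjamini-Hochberg adjustment (optimal for large-scale multiple hypothesis testing) at a false discovery rate of 5" (percent), "to account for multiple hypothesis testing between metabolites". Sections 6.1 and 6.2 assign Bonferroni to Aims 1b, 2a and 2b. The Synopsis and section 6.3 say only that one or the other method will be used.

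**Metabolites measured.** Section 2.1 adds a wider panel: "We will also measure other lipid metabolites involved in the inflammatory resolution process including thromboxanes, leukotrienes, prostaglandins" and further classes. Section 5 repeats this. Neither gives the number of lipids.

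**Matrices.** The Synopsis rationale aims to "establish the concentration of SPMs in plasma, serum and peripheral blood mononuclear cells (PBMCs) of obese subjects in response to dietary supplementation". The lists then differ:

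| Matrices named | Where |
|---|---|
| Plasma, serum, PBMCs | Synopsis (rationale, Aim 1a), 1.1, heading of Aim 1a in 2.1, 4.1, 5 |
| Plasma, PBMCs | Introduction to section 2, method text of Aim 1a in 2.1, 3.1 |
| PBMCs or serum | Synopsis, Efficacy Evaluations |

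The reason for using several matrices also varies. Section 2.1: "The rationale for PBMCs vs. plasma is to compare whether SPM levels in PBMCs are higher than plasma or vice versa". Section 5: "The rationale for PBMCs vs. plasma and serum is to compare biomarkers for SPM uptake". No section calls one matrix primary.

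**The concern.** The sizing and the analysis use different error rates for the same endpoint. A family-wise rate bounds the chance of even one false claim. BH bounds the expected share of false claims among those made. The two coincide when nothing is real and can part once something is. Section 6.1 itself describes BH as suited to large-scale testing and Bonferroni to smaller-scale testing. Three metabolites are small-scale, so the choice of BH suggests that the wider panel was in mind, but the text does not say so.

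The boundary of the family then decides what the primary analysis means:

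- If each matrix is adjusted on its own and none is primary, a reader cannot tell which result answers the primary question.
- If the whole panel is one family, the threshold for the three primary metabolites depends on how many other lipids are assayed and how many of them respond. The power statement took no account of this.

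**Working it through.** **Inputs.** From the plan: three metabolites, 5% family-wise, n=9, power above 80%, paired t-test, 18 raised to 24 (sections 6.1 and 6.4); two-tailed tests and BH at 5% (section 6.1). Assumed: a 0.05/3 split for sizing, exactly 80% power at n=9, independent tests unless stated, and panel sizes of 50 and 100.

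**1. The plan's own figure.** The power cannot be reproduced, because neither the SD nor the scale of the 50% change is given. Solving backwards with the noncentral t (8 df, two-sided 0.05/3 = 0.0167), 80% power needs a standardized within-subject effect of 1.32. The SD of differences must then be at most 0.50/1.32 = 0.38 on a relative scale, or ln(1.5)/1.32 = 0.31 on the log scale. At n=18 the same effect has 99.7% power. The inflation to 24 equals 18/(1 − 0.25).

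**2. BH over the three in one matrix.** The BH thresholds are 0.0167, 0.0333 and 0.05.

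- None real: 5%.
- One real and certain to be detected: a null is rejected if the smaller null p-value is at most 0.0333 or both are at most 0.05. The probability is 1 − (1 − 0.0333)² + (0.05 − 0.0333)² = 0.0656 + 0.0003 = 6.6%. Simulation with the effect of 1.32 gives 6.2% to 6.3% at n=9 and 6.5% to 6.7% at n=18; the excess of 6.7% over 6.6% is simulation error.
- Two real: the remaining null is tested at no more than 0.05, so at most 5% (simulated 4.8% to 4.9%).
- Three real: no null remains, so no false positive is possible.

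**3. Holm over the same three.** Family-wise error is 4.3% to 5.0% in simulation. Power per metabolite:

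| Truly changed | BH, n=9 | Holm, n=9 |
|---|---|---|
| 1 | 81% | 80% |
| 2 | 89% | 85% |
| 3 | 93% | 91% |

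At n=18 both exceed 99%.

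**4. Illustration: BH within each of three matrices, claim allowed from any.** With none real and independence: 1 − 0.95³ = 14.3%. With one of the three metabolites real and certain to be detected in every matrix: 1 − (1 − 0.0658)³ = 18.5%; simulation with the effect of 1.32 gives about 17.5% (n=9) to 18.7% (n=18). With an equal correlation between all differences:

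| Correlation | None real | One real per matrix |
|---|---|---|
| 0.6 | about 10% to 11% | about 14% |
| 0.9 | about 6% | about 8% |

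These count errors in both directions. Counting only false increases, the independent case falls to about 7.5% (none real) and 9.3% to 9.7% (one real).

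**5. Illustration: the whole panel as one BH family, only the three respond.**

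| Assumed panel | Power per metabolite, n=9 (one sex) | n=18 (pooled) |
|---|---|---|
| 50 | 39% | 97% |
| 100 | 26% | 94% |

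If a quarter of the panel responds, the n=9 figure is about 69%; if half does, about 84%.

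**The case against.** The strongest reply is that this changes little in practice. The three metabolites are named in advance. Every capsule contains all three compounds and the sizing expects each to rise, in which case no false positive among them is possible. Even the worst one-matrix case is under 7%. All of that stands, and it is why the FWER-versus-FDR mismatch alone is a small matter.

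A reader might infer from step 4 that the trial runs a false-positive rate of 14% to 19%. The documents do not support that. No section makes a rise in any one matrix a positive primary result; the either-matrix rule in the Synopsis governs only whether CyTOF goes ahead. Plasma and serum also come from the same draw, so independence is an upper case. Likewise, the 26% to 39% power figures need an assumed panel size, a panel in which nothing else responds, and a by-sex analysis that the plan holds in reserve.

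A reader might also take the either-method wording in the Synopsis and section 6.3 to leave the method open until the data are seen. Sections 6.1 and 6.2 settle it aim by aim, so only a cross-reference is needed.

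Finally, this is an uncontrolled pilot, and comparing PBMCs with plasma is part of Aim 1a's rationale. Keeping several matrices co-primary is therefore legitimate, provided the adjustment covers them. Pilot status does not remove the gap, because the plan itself sizes the primary endpoint on a 5% family-wise rate.

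**Conclusion.** The point holds in a limited form. The primary metabolites are defined; the primary matrix and the scope of the BH family are not, and BH does not guarantee the error rate on which the study was sized. On the narrowest reading the cost is an error rate of 6.2% to 6.7% instead of 5%, and only when exactly one of the three metabolites truly changes. The larger figures show what the open wording would permit. They are not the trial's actual error rate or power, and they rest on the assumptions of exactly 80% power at n=9, independence and invented panel sizes. Power at the pooled n=18 is high on every reading tabulated. Severity: minor to moderate, and best settled before analysis.

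**What to change.** In section 6.1 (Aim 1a) and the Synopsis, state:

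> Primary analysis of Aim 1a: pre-to-post change in 18-HEPE, 17-HDHA and 14-HDHA in [one matrix chosen by the sponsor before analysis], both sexes pooled, Holm-adjusted at a two-sided 5% family-wise error rate; analyses by sex are supportive. The same metabolites in the other matrices, and the PBMC versus plasma/serum comparison, are secondary and reported with estimates and confidence intervals. All other lipid metabolites are exploratory, with Benjamini-Hochberg at 5% FDR. Aim 1b keeps its own Bonferroni adjustment as stated.

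If the sponsor prefers co-primary matrices, apply Holm across all metabolite-by-matrix tests instead. With nine tests the strictest threshold is 0.05/9 = 0.0056. Power at that threshold is about 60% at n=9 and 98% at n=18, and Holm does at least as well.

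Make the matrix lists agree across the Synopsis and sections 1.1, 2, 2.1, 3.1, 4.1 and 5. In the Synopsis and section 6.3, replace the either-method wording with a reference to the adjustment stated for each aim.

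**Cost.** No extra subjects or assays. The other matrices become secondary. At n=9 Holm has up to about 4 points less power per metabolite than BH over the same three (85% against 89% with two real); at n=18 the difference is under 1 point. The sponsor should confirm that the SD used for sizing, a median across all metabolites in an earlier dataset, applies to the matrix chosen.
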